3.1 STUDY POPULATION

3.1.1 Population (base)

Patients (18 years and older) who have an indication for colonoscopy, in particular patients from the nationwide screening program.

3.1.2 Inclusion criteria

Inclusion criteria for participating endoscopists will be:

1. Experienced endoscopists (i.e. total number of colonoscopies performed will be at least 250 procedures under supervision plus 500 colonoscopies independently) including documentation of the key-performance indicators (cecal intubation rate, adenoma detection rate and polypectomy rate)

3.1.3 Exclusion criteria

No exclusion criteria.

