2. INTRODUCTION AND RATIONALE

Professionalism in the colonoscopy practice clearly changed the clinical course of colorectal cancer (CRC). Both CRC incidence and mortality continue to decline {Nishihara, 2013;Zauber, 2012}. With the introduction of the nationwide FIT-based CRC screening program, nearly 15,000 patients are yearly diagnosed with large (≥ 2 cm) complex (non-pedunculated) colorectal polyps (abbreviated as LNPCPs), for which endoscopic resection is the first-line therapy. The post-colonoscopy CRC rate did not drop over the past decade {Pullens, 2015;le Clercq, 2014}. Besides missed cancer/ precursors, incomplete polyp resection explains at least 20% of all PCCRCs {Robertson, 2014}, a situation which must be clearly improved.

Recent guidelines of gastrointestinal professional societies provide a conceptual basis to perform endoscopic treatment for LNPCPs {Pimentel-Nunes, 2015;Rutter, 2015}. In clinical practice, endoscopic resection outcomes vary and are far from perfect. As the nationwide screening program progresses, it is important to optimize performance and outcomes of endotherapy.

Two recent meta-analysis examined the local recurrence rate after endoscopic resection of large colorectal polyps {Belderbos, 2014;Ortiz, 2014}. Belderbos et al. showed local recurrence rates in 15% (95% CI: 12-19%) of cases after endoscopic resection of nonpolypoid neoplasms. Ortiz et al. reported a local recurrence rate of 13.1% after resection of both polypoid and nonpolypoid neoplasms. Several factors are associated with risk of local recurrence with the most common ones being proximal location, lesion size and shape {Moss, 2011}. Importantly, piecemeal (instead of en-bloc) resection is often associated with local recurrence (OR 4.39, 95% CI: 2.05-9.41; 20%, CI: 16-25%) {Ortiz, 2014;Belderbos, 2014}. Studies from Japan showed a 4-times more frequent recurrence rate for piecemeal resection of LSTs (granular type) than en-bloc resection {Oka, 2015}. Another meta-analysis on the efficiency and safety of endotherapy for large (≥ 20 mm) colorectal polyps showed that 8% (95% CI: 7-10%) of such patients required additional surgery because of a non-curative endoscopic resection. An important finding was that >90% of the recurrences could be successfully treated by additional endoscopic therapy {Hassan, 2015}.

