3.1.4 Sample size calculation

Based on meta-analysis data (1), we expect that the a priori risk for recurrence after endoscopic resection of LNPCPs is approximately 20% after 6 months (conservative estimates). We hypothesize that additional training will reduce this risk by 50%. In the initial version of this project proposal, we assumed that each therapeutic colonoscopist will perform endoscopic resection in at least 50 LNPCPs per year. In the revised version, we propose that 2 colonoscopists will participate per center. Taking into account a drop-out risk of 20%, inclusion of at least 35 LNPCPs per colonoscopist (70 LNPCPs per center) during 1.5 year will be achieved.

Because randomization is performed on a **cluster level** (center level instead of patient level) and patients are **nested** (randomly assigned) between colonoscopists, we determined the **Intraclass correlation coefficient (ICC)**, i.e. correlation of observations in different clusters (design effect). As reference for power calculation, we used the methodology proposed in a large cluster randomized trial in the UK (2). The ICCs in this study ranged from less than 0.01 to 0.05, with a mean of ± 0.015 . Several factors could influence the cluster design in the above-mentioned study (e.g. socioeconomic differences, differences in local available care, differences in housing between clusters). It is unlikely, however, that such factors influence the results in our study, which could lead to a higher ICC. Because of differences in observation between colonoscopists In our project, we expect to find interobserver variation in measurements. We therefore estimate an ICC of 0.025 which is within the range of previously reported data (2). Intuitively, the variation between colonoscopists is expected to be greater than between centers. For this reason, we will calculate the ICC at colonoscopist level. Of note, in the context of the nationwide CRC screening program, quality measures are standardized at both center and individual colonoscopist level.

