4.3 Study procedures

4.3.1 Standard optical training and registration (control group)

A training package will be developed to train endoscopists in optical diagnosis based on the features in the OPTICAL I model (Paris classification, location, depression, easy friability and advanced imaging (NBI or chromoendoscopy)). The training will also concern the recognition of recurrence in a post-EMR scar. All participants will register a standardized and pre-defined set of parameters within their endoscopy report for every colonoscopy where a LNPCP >20mm is encountered or removed (Appendix A).

Because size, morphology, site and access to a lesion predict the completeness of resection (SMSA score) {Rutter, 2015}, the difficulty of endoscopic resection will be stratified according to the SMSA score (Figure 1). The features of the SMSA score will also be included in the standardized set of parameters.

Photo documentation will be performed by the endoscopists at the following moments:

1. During lesion assessment
 - a. In white light
 - b. Zoom with advanced imaging (e.g. NBI, I-scan)
2. After performing the EMR
 - a. Scar before adjunctive treatment
 - b. Scar after adjunctive treatment/before adjuvant treatment
 - c. Scar after adjuvant treatment

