4.3.4 Data inclusion

All endoscopists will perform at least 35 consecutive endoscopic resections of LNPCPs. During the procedure, a tattoo will be placed 2 cm distal of the lesion at the same side, to make sure the scar can be found during the surveillance colonoscopy. Six months follow-up data will be collected for all cases. During this surveillance colonoscopy, endoscopists are asked to report whether there is recurrence and how this is treated. In addition, the scar will be photo documented in white light and zoom with advanced imaging (e.g. NBI, I-scan, blue light). Furthermore, the scar will be biopsied, with one biopsy every 5 mm (with the biopsies being presented to the pathology in separate jars).

Beyond this project proposal, we will monitor long-term (36 months) outcomes after endoscopic resection (i.e. local recurrence, referral to surgery). LNPCP patients will receive surveillance colonoscopy according to the Dutch post-polypectomy surveillance guideline {Dekker, 2013}.

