- b. Zoom
- c. Zoom with advanced imaging modality (e.g. NBI, I-scan)

STEP 2: ENDOSCOPIC MUCOSAL RESECTION

1. EMR documentation in endoscopy report

- a. Lifting fluid → NaCl / Gelofusin/ Venofundin

- b. Dye included in the injection fluid →yes/no
- c. Adjuvant adrenalin in lifting fluid → yes/no?
- d. En-bloc or piecemeal?
- e. Number of pieces [n = ... / >10 fragments]
- f. Intraprocedural bleeding yes/no?
 - i. Number of intraprocedural bleedings
 - ii. Treatment intraprocedural bleeding
 - 1. Clipping
 - 2. Snare tip coagulation
 - 3. Coagulation grasper
 - 4. Adrenalin injection
- g. Residual tissue after EMR yes/no?
 - i. In case of residual tissue, adjunctive treatment?
 - 1. Cold avulsion with biopsy forceps
 - 2. Cold avulsion with thermal ablation (CAST)
 - 3. Hot avulsion
 - 4. Snare tip coagulation
 - 5. Suck and snare
 - 6. APC
- h. Adjuvant treatment performed to prevent recurrence yes/no?
 - i. Argon plasma coagulation
 - 1. Borders (y/n)
 - 2. Scar surface (y/n)
 - ii. Snare tip soft coagulation
 - 1. Borders (y/n)
 - 2. Scar surface (y/n)

2. Tattoo 2 cm distal at the same side (to make sure the scar can be retrieved during surveillance colonoscopy)

3. Photo/videodocumentation

- a. Recording first 5 EMRs (intervention group)
- b. Photodocumentation of the scar
 - i. Before adjunctive treatment
 - ii. Before adjuvant treatment
 - iii. After adjuvant treatment

STEP 3: AFTER COLONOSCOPY

- 1. Informing the patient about the study

2. Providing the information package
3. Note patient data on study list (patient number, sex, birthdate)
4. Schedule 6 month FU colonoscopy

STEP 4: SURVEILLANCE COLONOSCOPY AFTER 6 MONTHS

1. Endoscopy report

- a. Recurrence yes/no?
- b. Unifocal or multifocal [n]
- c. Size of largest recurrence (in mm)
- d. In case of recurrence, treatment yes/no?
 - i. Re-EMR
 - ii. Cold avulsion
 - iii. Cold avulsion with snare tip coagulation (CAST)
 - iv. Hot avulsion
 - v. Suck and snare
 - vi. eFTR
 - vii. ESD
 - viii. APC
 - ix. Snare tip soft coagulation (STSC)

2. Biopsy the scar

- a. Take a biopsy every 5 mm [e.g. in a scar of 18mm, 3 biopsies are taken]
- b. Present every biopsy in a separate PA jar

3. Photodocumentation

- a. Scar [white light, zoom and advanced imaging modality]

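### Lesions with a previous resection attempt can enter the primary analysis, and no checklist item or model term identifies them

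*Protocol*

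**What the plan says.** Section 3.1.1 describes the base population as "Patients (18 years and older) who have an indication for colonoscopy, in particular patients from the nationwide screening program". Section 3.1.2 opens with "Inclusion criteria for participating endoscopists will be" and lists nothing about patients or lesions. Section 3.1.3 reads "No exclusion criteria".

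The only limit on the lesion is its definition in section 2: "large (≥ 2 cm) complex (non-pedunculated) colorectal polyps (abbreviated as LNPCPs". Accrual follows section 4.3.4: "All endoscopists will perform at least 35 consecutive endoscopic resections of LNPCPs".

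The primary model (section 5.1) contains study group, the endoscopist's previous experience and lesion complexity by SMSA. Section 4.3.1 introduces that score with "Because size, morphology, site and access to a lesion predict the completeness of resection (SMSA score". The sample size (section 3.1.4) rests on this premise: "we expect that the a priori risk for recurrence after endoscopic resection of LNPCPs is approximately 20% after 6 months", to be halved by training.

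Appendix A Step 4, the 6-month form, asks "In case of recurrence, treatment yes/no" and lists re-EMR among the treatments.

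**The concern.** A lesion that was already attempted, or that has regrown at an old scar, has a treatment history that the endoscopist under study did not create and that may affect its recurrence risk. The earlier attempt may have been made by someone outside the trial or in the other arm. The protocol lets such lesions count towards the 35 per endoscopist and towards the primary endpoint, but does not ask that they be marked.

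Two things are at stake. First, whole centres are randomised, 10 per arm in section 3.1.4 or 15 per arm in the Summary. Section 2 mentions referral of complex lesions to specialised centres, so case mix may plausibly differ by centre. With so few units, the share of attempted lesions can differ between arms by chance. Second, if training improves the outcome of a first resection more than that of a repeat one, attempted lesions dilute the effect the trial is powered to detect.

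A later analysis plan could not reliably repair this, because it cannot adjust for a variable that was not collected.

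**Working it through.** **1. Can these lesions enter?** Sections 3.1.1 to 3.1.3, the definition in section 2 and the consecutive rule in 4.3.4, read together, leave three conditions: an adult, an indication for colonoscopy, and a non-pedunculated lesion of at least 2 cm that is resected. None requires a previously untreated lesion, and none limits entries per lesion site.

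**2. Would they be identified?**

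| Source | Content | Previous attempt? |
|---|---|---|
| Appendix A Step 1, items a-j | location, access, size, Paris type, granularity, depression, bleeding, advanced imaging, optical diagnosis, certainty | no |
| Appendix A Step 2 | resection technique, bleeding, residual tissue, adjunctive and adjuvant treatment, tattoo, images | no |
| SMSA (4.3.1) | size, morphology, site, access | no |
| eCRF (7.1) | includes the indication for colonoscopy and the findings | some cases, indirectly |
| Model (5.1) | arm, endoscopist experience, SMSA | no |

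**3. The plan's own sample size.** Inputs from section 3.1.4: 20% vs 10%, power 90%, alpha 5% (taken as two-sided), ICC 0.025, m = 35, efficiency loss 10%, drop-out 20%.

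- n = [1.960·√(2·0.15·0.85) + 1.2816·√(0.2·0.8 + 0.1·0.9)]² / 0.10² = 265.9
- Design effect = 1 + 34 × 0.025 = 1.85
- 265.9 × 1.85 / 0.90 / 0.80 = 683 per group, as stated.

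The arithmetic is not in dispute. Effective n per arm = 683 × 0.80 × 0.90 / 1.85 = 265.8.

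**4. Spurious difference from unequal shares.** The documents give neither the share g of attempted lesions nor their recurrence rate r, so both are assumed. With no training effect, the rate in an arm is (1 − g) × 0.20 + g × r. The difference between arms is then (difference in g) × (r − 0.20). For shares of 15% and 5%:

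- r = 30%: 0.10 × 0.10 = 1 percentage point
- r = 40%: 0.10 × 0.20 = 2 percentage points

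**5. Power with equal shares.** Here untreated lesions recur in 20% vs 10%, and attempted lesions recur at r in both arms (no training effect in them). Power = Φ[(d − 1.96·SE₀)/SE₁], with pooled SE₀ and unpooled SE₁.

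Example, g = 10%, r = 40%: control 0.9 × 0.20 + 0.1 × 0.40 = 22%; intervention 0.9 × 0.10 + 0.1 × 0.40 = 13%; d = 0.09, SE₀ = 0.0330, SE₁ = 0.0327, power 78%.

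The Summary and section 4.2 plan 30 endoscopists per arm, so the second set of columns uses 30 × 35 = 1,050 lesions and an effective n of 1,050 × 0.80 × 0.90 / 1.85 = 408.6.

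| Share g | 265.8 per arm, r = 30% | 265.8, r = 40% | 408.6 per arm, r = 30% | 408.6, r = 40% |
|---|---|---|---|---|
| 0% | 90% | 90% | 98% | 98% |
| 5% | 85% | 85% | 96% | 96% |
| 10% | 80% | 78% | 94% | 92% |
| 20% | 67% | 64% | 85% | 82% |

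**6. The opposite assumption.** If training also halves recurrence in attempted lesions, power at 265.8 per arm is 91% to 95% over the same g and r. Nothing is lost.

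**The case against.** The strongest defence is that consecutive all-comers are a legitimate choice for testing training in routine practice. Section 3.1.4 speaks of resection of LNPCPs without saying first resection, so one cannot show that the planned 20% refers only to untreated lesions. Section 3.1.3 directly follows a list of criteria for endoscopists and may mean only that no endoscopists are excluded. All of this stands. It argues against demanding exclusion, but not against recording: under either reading nothing keeps attempted lesions out and nothing marks them.

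A second defence is that a chance imbalance between randomised centres is not systematic bias, and that the ICC and the random intercept allow for part of it. This is fair. The protection is partial, since the intercept is at colonoscopist level while referral patterns may belong to the centre. A baseline covariate would show the imbalance and allow adjustment.

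Three stronger readings are tempting and not supported:

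- *The trial's own recurrences re-enter and one failure is counted twice.* No rule bars re-entry, but the recurrent tissue would again have to meet the 2 cm definition, which is probably rare. Appendix A handles a recurrence as an outcome in Step 4, and nothing says that its treatment opens a new Step 1. The site log makes a returning patient traceable. A second event would be a second failure. The real issue would be correlated entries from one site.
- *These lesions can never be found afterwards.* The indication for colonoscopy in the eCRF would reveal some of them, though it need not state an earlier attempt at that site.
- *Power will fall to 64%.* That figure needs a 20% share, 40% recurrence, no training effect in these lesions and the smaller of the two planned sizes.

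**Conclusion.** The point holds as a gap in eligibility and data capture. Previously attempted lesions can enter the primary analysis. They are not recorded as such, and the stated model cannot adjust for them. With 10 to 15 centres per arm, an imbalance could go largely unseen.

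The size is unknown. Under the assumed shares of 5% and 15% and recurrence of 30-40%, the distortion is 1 to 2 points against a planned difference of 10. Power loss is conditional: with no training effect in these lesions it ranges from small to substantial, depending on their share and on which planned size applies, and it vanishes if training works equally well in them. A reader might infer that the primary endpoint is in fact contaminated, but the text shows only that mixing is possible. The point does not challenge the figure of 683 per group and does not make the all-comers design wrong. It is worth correcting because it is cheap now and may not be recoverable once the procedures are done.

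**What to change.** - **Appendix A Step 1 and the eCRF:** add *previous resection attempt at this site: yes/no*.
- **Section 5.1:** pre-specify this item as a covariate in the primary model, with a sensitivity analysis in lesions without a previous attempt.
- **Section 4.3.4:** state that each lesion site enters once, so that a recurrence of a trial lesion is an outcome and not a new case.
- **Section 3.1.3:** say whether the sentence refers to endoscopists, lesions or both.

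The sponsor may instead exclude previously attempted lesions from the primary analysis. This trades a narrower population and some countable lesions for a cleaner question, and it is not required.

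The cost of the recommended change is one extra field, one extra model term and two clarifying sentences.

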3.1.4 Sample size calculation

Based on meta-analysis data (1), we expect that the a priori risk for recurrence after endoscopic resection of LNPCPs is approximately 20% after 6 months (conservative estimates). We hypothesize that additional training will reduce this risk by 50%. In the initial version of this project proposal, we assumed that each therapeutic colonoscopist will perform endoscopic resection in at least 50 LNPCPs per year. In the revised version, we propose that 2 colonoscopists will participate per center. Taking into account a drop-out risk of 20%, inclusion of at least 35 LNPCPs per colonoscopist (70 LNPCPs per center) during 1.5 year will be achieved.

Because randomization is performed on a **cluster level** (center level instead of patient level) and patients are **nested** (randomly assigned) between colonoscopists, we determined the **Intraclass correlation coefficient (ICC)**, i.e. correlation of observations in different clusters (design effect). As reference for power calculation, we used the methodology proposed in a large cluster randomized trial in the UK (2). The ICCs in this study ranged from less than 0.01 to 0.05, with a mean of ± 0.015 . Several factors could influence the cluster design in the above-mentioned study (e.g. socioeconomic differences, differences in local available care, differences in housing between clusters). It is unlikely, however, that such factors influence the results in our study, which could lead to a higher ICC. Because of differences in observation between colonoscopists In our project, we expect to find interobserver variation in measurements. We therefore estimate an ICC of 0.025 which is within the range of previously reported data (2). Intuitively, the variation between colonoscopists is expected to be greater than between centers. For this reason, we will calculate the ICC at colonoscopist level. Of note, in the context of the nationwide CRC screening program, quality measures are standardized at both center and individual colonoscopist level.

After correction for the design effect ($= 1+(m-1)*ICC$, where $ICC = 0.025$ and the mean number of patients per colonoscopist is 35, i.e. $m = 35$), 10% loss in efficiency due to the variation in the number of colonoscopies performed during the study period per colonoscopist (3), and a 20% drop-out risk for patients with LNPCP, the number of LNPCP cases required to detect a difference of 10% (20% local recurrence in the control group vs 10% in the intervention group) with a power of 90% and using a significance level alpha of 5% is 683 per group. This means that 20 colonoscopists per group are required. In the revised protocol, we have increased the power of analyses from 80% to 90%. In conclusion, in the 20 participating centers (10 per arm), a total of 20 colonoscopists will perform approximately 35 endoscopic resections each over 1.5 year.

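### Section 3.1.4 sizes a centre-randomised trial with a colonoscopist-level design effect, so 90% power at 683 per group holds only if the two colonoscopists of a centre are uncorrelated

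*Protocol*

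**What the plan says.** Protocol 4.2 and the summary randomise centres, with two endoscopists in each, to limit exchange of knowledge and skills between participants. Section 3.1.4 repeats that randomisation is at centre level and expects that "inclusion of at least 35 LNPCPs per colonoscopist (70 LNPCPs per center) during 1.5 year will be achieved".

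The same section then works one level down. It expects colonoscopists to vary more than centres and concludes: "For this reason, we will calculate the ICC at colonoscopist level". The value follows from expected differences in observation between colonoscopists: "We therefore estimate an ICC of 0.025 which is within the range of previously reported data (2". The design effect is 1 + (m − 1) × ICC, where "the mean number of patients per colonoscopist is 35". The difference to be detected is "20% local recurrence in the control group vs 10% in the intervention group". After a 10% efficiency loss for unequal numbers and 20% drop-out, the section puts the requirement at 683 lesions per group, for 90% power at a 5% alpha. It stresses that power was raised from 80% to 90%.

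No correlation between the two colonoscopists of a centre is given. The primary model in sections 5 and 5.1 likewise has a random intercept for colonoscopists only.

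**The concern.** A design effect has to reflect the unit that is randomised. When both colonoscopists of a centre go to the same arm, anything their lesions share (referral mix, equipment, pathology, local habits) adds to the variance of the arm comparison. A factor built on 35 lesions per colonoscopist leaves that part out, and is the factor for a trial that randomises colonoscopists.

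The stated reason does not close the gap. More variation between colonoscopists than between centres is compatible with any moderate centre-level correlation; it does not make that correlation zero. The reason given for randomising centres, that colleagues exchange knowledge and skills, makes some within-centre similarity plausible.

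At stake is the 90% power, which the section states without condition.

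**Working it through.** **Inputs from section 3.1.4:** recurrence 20% vs 10%; alpha 5% (sidedness not stated; two-sided reproduces the figure); power 90%; ICC 0.025; 35 lesions per colonoscopist; 70 per centre; efficiency factor 0.9; retention 0.8.

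**Reproducing 683.** The pooled-variance two-proportion formula gives

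n = [1.96 × √(2 × 0.15 × 0.85) + 1.2816 × √(0.2 × 0.8 + 0.1 × 0.9)]² / 0.10² = 265.86 per group.

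Design effect: 1 + (35 − 1) × 0.025 = 1.85.

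265.86 × 1.85 / 0.9 / 0.8 = 683.1.

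The stated figure reproduces, so the arithmetic is sound. Also 683 / 35 = 19.5, hence 20 colonoscopists per group.

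**Design effect for randomised centres.** Let r1 be the correlation between two lesions of the same colonoscopist, and r2 the correlation between lesions of the two colonoscopists of one centre. With 35 lesions each,

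DE = 1 + (35 − 1) × r1 + 35 × r2.

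This equals 1.85 only at r2 = 0. At r2 = r1 = 0.025 it equals 1 + 69 × 0.025 = 2.725, the ordinary formula with m = 70. In a nested variance-component model r1 contains the centre part, so r2 cannot exceed r1, and 0.025 is the upper bound.

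**Power at 683 per group**, with r1 = 0.025 and effective n = 683 × 0.8 × 0.9 / DE. The values of r2 are assumptions.

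| r2 (assumed) | DE | Effective n | Power | Needed per group for 90% |
|---|---|---|---|---|
| 0 | 1.850 | 265.8 | 90.0% | 683 |
| 0.005 | 2.025 | 242.8 | 87.2% | 748 |
| 0.01 | 2.200 | 223.5 | 84.4% | 813 |
| 0.0125 | 2.288 | 215.0 | 83.0% | 845 |
| 0.025 | 2.725 | 180.5 | 76.0% | 1,007 |

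**Cluster size counted after drop-out.** With 35 × 0.8 = 28 analysed lesions per colonoscopist, DE = 1 + 27 × 0.025 + 28 × r2 = 1.675 + 28 × r2. Power is 92.6% at r2 = 0. DE returns to 1.85 at r2 = 0.175 / 28 = 0.006, so 90% holds up to about there. At r2 = 0.0125 DE is 2.025 and power 87.2%; at 0.025 DE is 2.375 and power 81.6%.

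**The larger plan.** The summary and section 4.2 name 30 endoscopists per arm, and the summary 15 centres per arm. At 35 lesions each that is 1,050 per arm. With DE 2.725 the effective n is 1,050 × 0.72 / 2.725 = 277.4 and power is 91.2%.

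**The case against.** The level of the ICC was a disclosed choice with a reason attached. By that reason 0.025 is a colonoscopist-level quantity and is correctly paired with m = 35. This stands as far as it goes: r1 = 0.025 with m = 35 is a proper part of the calculation. It does not supply the missing centre term.

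A reader might infer that 0.025 was taken over from the cited UK cluster trial as an ICC for the randomised unit, and so belongs with m = 70. The text does not support this. It puts that trial's mean near 0.015, says the area-related factors there are unlikely to operate here, ties 0.025 to differences between colonoscopists and notes only that it lies within the trial's range. If 0.015 were used as a single centre-level ICC, DE would be 1 + 69 × 0.015 = 2.035 and power 87.1%.

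A reader might also infer that the trial delivers 76–83% power. That presupposes r2 between 0.0125 and 0.025, which appears nowhere in the protocol. If the protocol's expectation means that the colonoscopist variance component exceeds the centre component, r2 is below half of r1, that is below 0.0125, and power lies between 83% and 90%.

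There may also be slack. Section 3.1.4 mentions the 20% drop-out when it arrives at 35 per colonoscopist and then allows for it again in the 683. If 35 is already net of drop-out, 20 colonoscopists give 700 analysable lesions per group. Effective n is then 700 × 0.9 / 2.288 = 275 at r2 = 0.0125 (91% power) and 700 × 0.9 / 2.725 = 231 at r2 = 0.025 (86%). The wording allows this reading but does not establish it.

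**Conclusion.** The point holds in conditional form. The figure of 683 is correctly computed, but it supports 90% power only under an unstated assumption of no correlation between the two colonoscopists of a centre. The reason offered does not justify that assumption. On the protocol's own cluster size, power at 683 per group runs from 90.0% at r2 = 0 to 76.0% at r2 = 0.025; with cluster size counted after drop-out, from 92.6% to 81.6%. The documents do not say where in that range the trial lies, so a definite shortfall is not shown. All figures rest on the normal approximation, r1 = 0.025 and the protocol's own drop-out and efficiency allowances.

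This should be fixed, but it does not threaten the trial if 30 endoscopists per arm take part, because that size keeps about 91% power even at the upper bound. It matters more if section 3.1.4 governs. That section asks for 20 colonoscopists per group and then closes with 20 in total across 20 centres, although two in each of 20 centres would be 40.

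**What to change.** - Rewrite the calculation in 3.1.4 with the centre as the randomised unit. State r1 and r2 with a reason for each, and use DE = 1 + (35 − 1) × r1 + 35 × r2.
- State whether 35 is before or after drop-out, and apply the 20% once.
- Replace the unconditional 90% by the power over a range of r2, such as the table above, with r2 labelled as an assumption.
- Reconcile the 20 colonoscopists per group, and the total of 20, in 3.1.4 with the 15 centres and 30 endoscopists per arm in the summary and the 30 per arm in 4.2. If the larger number is the plan, say so and give its power: about 91% at r2 = 0.025.
- Check that the clustering assumed here matches the random effects in section 5.1.

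The cost is a rewritten paragraph and one small table. If the larger plan stands, no recruitment is needed beyond the 60 endoscopists the protocol already names.
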